6.4.5 Other Efficacy Analysis

All analyses of the 5-Point Likert Scale for conspicuity and CEF will be conducted using conspicuity assessments mapped to time points using the windowing algorithm described in Section 6.8.1.

Subgroup analysis will be conducted on the primary endpoint, key secondary endpoints and color contrast quantitative assessment (CEF) within the ITT population. Data imputation described in the analysis of the primary and key secondary endpoints will also be applied to the subgroup analysis.

The endpoints listed above will be summarized using descriptive statistics within the following subgroups:

- BMI (underweight or normal, $<25 \text{ kg/m}^2$; overweight, ≥ 25 to $<30 \text{ kg/m}^2$; obese, $\geq 30 \text{ kg/m}^2$)
- Prior pelvic or abdominal surgery (yes; no)
- Prior inflammatory disorder (yes; no)
- Type of surgery (gynecological; other abdominopelvic)
- Type of surgery (minimally invasive only; open only; minimally invasive and open)
- Type of device (1688; SPY-PHI; Other)
- Sex (female; male)
- EudraCT Age (≥ 12 and <18 ; ≥ 18 and <65 ; ≥ 65 to <85 ; ≥ 85)
- Ethnicity (Hispanic or Latino; Not Hispanic or Latino)
- Race (American Indian or Alaska Native; Asian; Black or African American; Native Hawaiian or Other Pacific Islander)

Summaries by surgeon will also be presented.

Further, the following analyses of conspicuity data will only use observed records mapped to time points using the windowing algorithm but will not have data imputation applied.

The descriptive summaries of the primary end point, key secondary endpoints and CEF will be repeated using data collected from non-index ureters on participants in the ITT population.

Descriptive statistics for the number of NIR-F conspicuity time points for each participant during surgery will be presented.

Descriptive statistics for WL and NIR-F conspicuity scores will be presented by time point for the ITT and mITT populations. A line chart displaying the NIR-F and WL scores by time point will be provided for the mITT population.

The frequency and percentage of participants with each WL and NIR-F conspicuity score will be presented by time point for the ITT and mITT populations. This will be repeated for the non-index ureter for the ITT population.

The frequency and percentage participants who experience ICES throughout the study will be presented for the ITT and mITT populations. The specific categories and subcategories will be as follows:

- Any ICE
- ICE1 Total
 - ICG unless used for anastomotic evaluation after the ureters have been visualized or for lymphatic mapping where there is a clear anatomic separation of the ureters and lymphatics
 - Other NIR-F imaging agents
 - Ureteral stent
- ICE2 Total
 - ICE2, first conspicuity assessments collected after 30-min window
 - ICE2, first conspicuity assessment collected in 30-min window but either WL or NIR-F not collected
 - ICE2, no conspicuity assessments collected

A listing of ICEs will be provided. And a swimmer plot displaying NIR-F conspicuity scores for the index ureter and assessments impacted by ICEs for each patient will be provided.

6.5 Analysis of Safety

Safety analyses will be conducted on the SAF and will be presented within the participant groups listed in Section 6.1 unless otherwise specified. No hypothesis testing will be performed.

6.5.1 Adverse Events

AEs will be coded using MedDRA and graded using the National Cancer Institute-common terminology criteria for AE (NCI-CTCAE, version 5.0).

A TEAE is defined as an AE observed after administration of the IP and up to the follow-up period. A drug-related TEAE is defined as any TEAE with a causal relationship assessed as “yes” by the investigator.

An overview summary table will include number and percentages of participants with TEAEs, drug-related TEAEs, serious TEAEs, drug-related serious TEAEs, TEAEs leading to death, drug-related TEAEs leading to death and of all deaths. Frequencies and percentages of ADEs, TEAEs and drug-related TEAEs by worst NCI-CTCAE will also be presented in the overview.

The number and percentage of participants with TEAEs, drug-related TEAEs, serious TEAEs and drug-related serious TEAEs will be summarized by SOC and PT. The number and percentage of TEAEs by NCI-CTCAE grade will also be summarized. The worst toxicity grade will be summarized if the same AE is recorded more than once for a participant. The number and percentage of participants with ADEs will be summarized by SOC and PT separately from TEAEs.

If a participant has multiple TEAEs with the same SOC or PT, but with differing CTCAE grade, then the participant will be counted once with the worst nonmissing grade. If a participant has multiple TEAEs with the same SOC or PT, but with differing relationship, then the participant will be counted once with the highest degree of relationship. If grade is missing for all episodes of the event, the participant will be counted under missing severity. If relationship is missing for all episodes of the event, the TEAE will be counted as related to study drug.

The number and percentage of TEAEs occurring in at least 5% of all participants in the SAF will be summarized by SOC and PT.

All AE data will be listed.

6.5.1.1 Adverse Events of Special Interest

Hypersensitivity and IUI-associated events will be considered adverse events of special interest (AESIs). The frequency and percentage of participants with each type of AESI will be summarized within the participant groups listed in Section 6.1. 95% Clopper-Pearson confidence intervals for the proportion of participants with each type of AESI will be presented.

AEs of special interest will be identified using all Preferred Terms (PT) from Standardized MedDRA queries (SMQ), see [Table 1](#).

Table 1 Standardized MedDRA Queries for AESIs

AESI	MedDRA SOC/PT coding or SMQs
Hypersensitivity	Hypersensitivity SMQ - Narrow search
Iatrogenic ureteral injury (IUI)	Iatrogenic injury PT - 10061213 Ureteric injury PT - 10046405 Ureteric rupture PT - 10049810 Ureteric perforation PT - 10065809 Urinary tract injury PT - 10061397

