## **2 INTRODUCTION**

### **2.1 Study Rationale**

ASP5354 (also known as pudexacianinium chloride) is a novel near-infrared fluorescence (NIR-F) imaging agent under investigation for intraoperative anatomical identification/visualization of ureter(s) in participants undergoing minimally invasive and open abdominopelvic surgeries.

Pudexacianinium chloride is a new chemical entity which has unique hydrophilic properties through conjugation with cyclodextrin. Unlike ICG, ASP5354 is iodine free. ASP5354 is administered intravenously and has a clinically distinct pharmacokinetic profile that allows for ASP5354 to be excreted into the urine through the kidneys. Photo-optically, ASP5354 is indistinguishable from ICG with an absorption of 780 nm and a fluorescence emission at 820 nm, allowing for the use of approved (ICG) NIR-F imaging technology. In this study, ASP5354 will be used with FDA-cleared imaging devices that have been approved for use with ICG for laparoscopic (Stryker 1688 Advanced Imaging Modalities device) and open surgical procedures (Stryker SPY-PHI). These devices provide both white light (WL) and NIR-F illumination modes. The NIR-F illumination/imaging technology when used with ASP5354 facilitates anatomic ureter visualization during minimally invasive and open abdominopelvic surgeries.

This study is designed to evaluate the clinical utility of ASP5354 which enhances the conspicuity of the ureter with the use of an NIR-F imaging device. The benefit of enhanced conspicuity is to identify the ureter as soon as possible during the surgical procedures, which is expected to help minimize the risk of iatrogenic ureteral injury (IUI) and associated complications. To date, there are no uniform prevention guidelines to avoid IUIs and no commercially available ureteral imaging agents. The European Association of Urology and American Society of Colon and Rectal Surgeons recommend either the use of ureteral stents and/or a cautious dissection with direct identification/visualization of the ureters during abdominopelvic procedures. Despite these recommendations, IUIs still occur and may not be evident until post-surgery. The European Association of Urology states that the best way to avoid IUIs is real-time ureter visualization. The use of ASP5354 with NIR-F imaging technologies is a promising technique that offers real-time ureter visualization for surgeons.

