### **7.3.6 Adverse Events of Special Interest**

Selected non-serious and serious AEs, also known as AESI, are to be collected via the SAE worksheet and reported to the sponsor within 24 hours of awareness.

In this study, the following are considered AESI:

- Hypersensitivity events (see [Section 2.3.1])
- IUI-associated events (see [Section 2.2])

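### SAP 6.5.1.1 counts iatrogenic ureteral injury from five coded terms, two of them not specific to the ureter, and does not link the count to the IUI events that investigators report

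*SAP*

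**What the plan says.** Protocol 7.3.6 names two AESI categories, hypersensitivity events and IUI-associated events. It sets a reporting route for both: "Selected non-serious and serious AEs, also known as AESI, are to be collected via the SAE worksheet and reported to the sponsor within 24 hours". Protocol 9.3.5.1 plans a frequency, a percentage and a Clopper-Pearson interval for each category, without saying how cases are identified.

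SAP 6.5.1.1 supplies the identification rule: "AEs of special interest will be identified using all Preferred Terms (PT) from Standardized MedDRA queries (SMQ"), with a pointer to its Table 1. The IUI row of that table names no standardized query. It lists five single Preferred Terms:

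- "Iatrogenic injury PT - 10061213"
- "Ureteric injury PT - 10046405 Ureteric rupture PT - 10049810 Ureteric perforation PT - 10065809" (three terms)
- "Urinary tract injury PT - 10061397"

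SAP 5.5.1 names the endpoint as participants with iatrogenic ureteral injury. No section of the SAP uses the SAE worksheet report, reconciles it with Table 1, or provides for medical review of the events that Table 1 picks up.

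**The concern.** The same AESI is identified in two ways. Investigators report it case by case on clinical judgment; the SAP tabulates it from coded terms. There is no rule for cases where the two disagree, and they can disagree in both directions.

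- **Too many.** Every participant has abdominopelvic surgery. An operative injury to another structure, if coded to the term that names no organ or to the general urinary tract term, would be tabulated as a ureteral injury.
- **Too few.** The list has no term for ureteral obstruction, leak or fistula. Protocol 2.1 notes that "IUIs still occur and may not be evident until post-surgery". A late-presenting injury could be reported as an IUI-associated AESI, be coded to a term outside the five, and not enter the count.

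Reducing ureteral injury is the clinical rationale for the product (Protocol 2.1, 2.2 and 2.3.2). The proportion and interval in this row are therefore likely to be read closely, and they may not match the AESI cases the sponsor already holds.

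**Working it through.** **Step 1. Classify the five terms by name.** Three name the ureter (injury, rupture, perforation). One names no organ. One covers the urinary tract as a whole. So 2 of 5 do not by themselves establish the event that SAP 5.5.1 names.

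**Step 2. Look for a link to the investigator report.** The protocol category is "IUI-associated events (see [Section 2.2"), defined only by a pointer to the background section. SAP 5.5.1 identifies adverse device effects from an investigator flag in the eCRF, but gives AESIs no equivalent. SAP 6.2.3 plans a review before database lock that may add terms for prior inflammatory disorders; SAP 6.5.1.1 has no such step.

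**Step 3. Inputs for size.**

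- Planned enrollment: 84 + up to 10 + 13 = 107 (SAP 2.2). If no renally impaired adults are enrolled: 84 + 13 = 97.
- Background rate: 643/53 096 = 1.21% (Protocol 2.2, hysterectomy).
- The documents give no power or precision figure for IUI to reproduce.

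**Step 4. Exact intervals, using the SAP's own method.** For x events in n participants, the lower limit is the 2.5th percentile of Beta(x, n − x + 1) and the upper limit is the 97.5th percentile of Beta(x + 1, n − x). For x = 0 the lower limit is 0.

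| Events | n = 107: estimate (95% CI) | n = 97: estimate (95% CI) |
|---|---|---|
| 0 | 0% (0 to 3.39%) | 0% (0 to 3.73%) |
| 1 | 0.93% (0.02 to 5.10%) | 1.03% (0.03 to 5.61%) |
| 2 | 1.87% (0.23 to 6.59%) | 2.06% (0.25 to 7.25%) |
| 3 | 2.80% (0.58 to 7.98%) | 3.09% (0.64 to 8.77%) |

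One reclassified participant moves the estimate by 1/107 = 0.93 points, or 1/97 = 1.03 points.

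**Step 5. Likely number of events, under an assumption.** If the hysterectomy rate applied to this mixed surgical population, the expected count is 107 × 0.0121 = 1.3, and the chance of at least one event is 1 − (1 − 0.0121)^107 = 73%. With 97 participants the figures are 1.2 and 69%. At that level, one case wrongly included or left out is nearly as large as the cited rate itself.

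**The case against.** The strongest reply is that both mechanisms depend on MedDRA coding, which the documents do not show. Nothing in them establishes that a bowel or vessel injury would code to the general iatrogenic term, or that a ureteral leak would code outside the list. Protocol 10.3.6 also asks for the diagnosis rather than signs or symptoms whenever possible, which should steer recognized ureteral injuries to a ureteral term and other injuries to their own. This stands as a limit: the documents support *can*, not *will*, and give no frequency. It does not supply the missing rule.

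A reader might infer that the SAP excludes investigator reports, or that reported injuries would disappear from the results. The documents support neither. The SAP is silent on the worksheet. AEs are also recorded in the eCRF (Protocol 7.3.1), summarized by system organ class and Preferred Term, and listed (SAP 6.5.1). What is uncertain is whether an event enters the IUI row. A listing does not correct that row's proportion or interval.

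The list can also be defended as deliberately sensitive, since *IUI-associated* is wider than confirmed injury. That partly justifies the two broad terms, but SAP 5.5.1 uses the narrower name, and breadth does not answer the risk of omission. The term list was revised in SAP version 3.0, and updates are allowed until database lock. That leaves room for a correction but does not change the current rule.

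A reader might also take one shifted case as changing a safety comparison. Both randomized arms receive ASP5354, SAP 6.5 plans no safety hypothesis tests, and the intervals above overlap heavily.

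**Conclusion.** The point holds as a definitional weakness worth correcting. The IUI row can include non-ureteral injuries and can omit investigator-reported ureteral injuries coded to other terms. Each such participant moves the estimate by about 0.9 percentage points at n = 107, or about 1.0 at n = 97. The expected count of about 1.3 rests on applying a hysterectomy rate to gynecological and other abdominopelvic surgery that includes adolescents; that is an assumption made to show scale. The frequency of misclassification is unknown.

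The consequence is confined to a descriptive safety summary. The primary and key secondary efficacy tests are unaffected. The point is limited to IUI: the hypersensitivity row uses a named standardized query, and no comparable problem with its terms is shown here.

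**What to change.** In SAP 5.5.1 and 6.5.1.1:

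1. Count as IUI any event with a ureter-specific term (ureteric injury, rupture or perforation), plus any event the investigator reported on the SAE worksheet as an IUI-associated AESI.
2. Count the general iatrogenic injury and urinary tract injury terms only when the verbatim term or the AESI report names the ureter.
3. Reconcile the worksheet AESIs with the term list before database lock, and document the outcome for each discrepant event.
4. Show the term-based and investigator-reported counts side by side.

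The cost is SAP wording, a short medical review, and a safety-database reconciliation for a handful of events. The reconciliation may need some manual work: Protocol 10.3.7 has worksheets sent by fax or email, and the documents show no AESI flag in the eCRF. The rule also brings in investigator judgment on a category that the protocol does not define closely; the side-by-side counts make that reliance visible.

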6.5.1.2 Green Coloration of Urine

The frequency and percentage of participants who experience green coloration of urine will be summarized within the participant groups listed in Section 6.1.

Green coloration of urine will be identified using all Preferred Terms (PT) from Standardized MedDRA queries (SMQ), see [Table 2](#).

Table 2 Standardized MedDRA Queries for Green Coloration of Urine

Event	MedDRA SOC/PT coding or SMQs
Green coloration of urine	Lower Level Terms (LLTs) that fall under Chromaturia PT – 10008796 Chromaturia LLT - 10008796 Urine color abnormal LLT - 10064752 Urine colour abnormal LLT - 10064748 Discoloration urine green LLT - 10070811 Discolouration urine green LLT - 10070812 Urine coloring green LLT - 10070848 Urine colouring green LLT - 10070862 Urine discoloration LLT - 10046628 Urine discolouration urine LLT - 10046629 Discoloration urine LLT - 10013080 Discolouration urine LLT - 10056126

6.5.2 Clinical Laboratory Evaluation

For quantitative clinical laboratory measurements (hematology, biochemistry, urinalysis), descriptive statistics will be used to summarize results and change from baseline by time point within the participant groups listed in Section 6.1. Postoperative laboratory values collected after surgery on Day 1 and postoperative laboratory values collected on Day 2 will be considered separate time points in the summary tables.

Quantitative laboratory test results by NCI-CTCAE Grade (version 5.0) will be summarized with frequencies and percentages by time point. Shift from baseline to the post-baseline worst grade based on NCI-CTCAE until the follow-up period in laboratory tests will be tabulated.

Table 3 Lab Parameters with CTCAE Grading

Panel/Assessments	Parameters with CTCAE Grading
Hematology	Eosinophils Hemoglobin Leukocytes Lymphocytes Neutrophils Platelets
Biochemistry	Albumin Alanine aminotransferase Alkaline phosphatase Aspartate aminotransferase Creatinine Creatinine kinase Gamma-glutamyl transferase Glucose Lactate dehydrogenase Magnesium Potassium Sodium

Panel/Assessments	Parameters with CTCAE Grading
	Total bilirubin Total cholesterol Triglycerides

All laboratory data will be listed.

6.5.2.1 Liver Safety Assessment

The liver safety assessments will be summarized by the following categories below based on the measurements from Alkaline Phosphatase (ALP), Alanine Transaminase (ALT), total bilirubin, Aspartate Transaminase (AST) and their combination.

The participant's highest value post-baseline of each parameter will be used; (upper limit of normal (ULN)).

- ALT: > 3xULN, > 5xULN, > 10xULN, > 20xULN
- AST: > 3xULN, > 5xULN, > 10xULN, > 20xULN
- ALT or AST: > 3xULN, > 5xULN, > 10xULN, > 20xULN
- ALP: > 1.5xULN
- Total Bilirubin: > 2xULN
- (ALT or AST > 3xULN) and Total Bilirubin > 2xULN
- (ALT or AST > 3xULN) and Total Bilirubin > 2xULN and ALP < 2xULN

6.5.3 Vital Signs

Descriptive statistics will be used to summarize vital sign results and changes from baseline within the participant groups listed in Section 6.1 and time point.

Tables for potentially clinically significant vital signs will be generated using baseline value and worst value obtained post-baseline for each participant. If the criterium is checking for values greater (or equal) to a specific value, the worst value is referring to the highest value obtained. If the criterium is checking for values less (or equal to) a specific value, the worst value is referring to the lowest value obtained. If the criterium is a combination of two conditions, the conditions need to be fulfilled for values obtained on the same post-baseline time points to meet the criterium.

The following potentially clinically significant criteria are defined for each parameter:

Vital Sign Variable	Criteria
SBP	≥ 180 mmHg AND ≥ 20 mmHg change from baseline
SBP	≤ 80 mmHg
DBP	≥ 105 mmHg AND ≥ 15 mmHg change from baseline
Pulse Rate	≥ 120 bpm AND ≥ 15 bpm change from baseline

All vital signs data will be listed.

6.5.4 Electrocardiogram and Cardiac Monitoring

Number and percentage of participants with normal, abnormal not clinically significant and abnormal clinically significant results for the overall interpretation will be tabulated within the participant groups listed in Section 6.1. A shift analysis table showing shift in overall interpretation from baseline to each time point will be provided.

Standard 12-lead ECG interpretations will be listed.

6.5.5 Pregnancies

A listing of all pregnancies will be provided.

6.5.6 Other Safety Analysis

Descriptive statistics for the duration of the surgical procedure in minutes will be presented.

Descriptive statistics for the time between ASP5354 dosing and the first conspicuity assessment will be presented.

6.6 Analysis of Pharmacokinetics

The analysis of the pharmacokinetics will be reported by the following 5 groups of participants.

- Adults with normal/mild eGFR (eGFR \geq 60 mL/min): WL/NIR-F arm
- Adults with normal/mild eGFR (eGFR \geq 60 mL/min): WL-only arm
- Adults with moderate renal impairment (eGFR \geq 30 to $<$ 60 mL/min): WL/NIR-F arm
- Adults with severe renal impairment (eGFR \geq 15 to $<$ 30 mL/min): WL/NIR-F arm
- Adolescent cohort (eGFR \geq 60 mL/min): WL/NIR-F arm

Plasma and urine concentrations will be mapped to time points using the windowing algorithm described in Section 6.8.1.

For ASP5354 in plasma, descriptive statistics will be used to summarize plasma concentrations for ASP5354 by time point. Individual overlay (spaghetti) and mean plasma concentration-time profiles (linear and semi-logarithmic scale) will be produced.

For ASP5354 in urine, descriptive statistics will be used to summarize urine concentrations for ASP5354, urine volume, amount excreted into urine (Ae), cumulative amount excreted into urine by time interval, duration of urine collection interval and urine production rate (mL/min).

Urine volume at a time point will be calculated by dividing the urine weight in grams by 1.018. Urine weight will be calculated as the difference between the full urine bag weight (g) and the empty urine bag weight (g).

Individual overlay (spaghetti) and mean cumulative amount of ASP5354 excreted into urine-time profiles will be produced.

Ae and the percentage of ASP5354 dose excreted into urine (Ae%) during surgery will be summarized.

Participants with ‘unable to void’ reported on the urine collection eCRF at a time point will have their urine weight imputed as 0 g and their urine volume reported as 0 mL for the analysis. Participants with a reported urine weight that is negative will have their urine weight imputed as 0 g.

Pharmacokinetic data will be listed.

Plasma and urine concentration data of ASP5354 will be subjected to population pharmacokinetic analysis and the similarity of pharmacokinetic profiles will be investigated by comparing adults and adolescents.

Details of the population analyses will be described in a separate analysis plan and a separate report.

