### 7.4.2 Analysis of ASP5354 in Urine

Urine samples for the analysis of ASP5354 in urine will be collected at the intervals indicated in the Schedule of Assessments [Table 1] and Sample Collection Schedule for Pharmacokinetics [Table 3].

A urethral catheter will be inserted before the administration of ASP5354 until the actual end of surgery. While the catheter is in place, each interval sample will be collected in a separate collection bag. Aliquots of urine samples will be collected from each collection bag. The time of ASP5354 administration, beginning of urine collection and exchange of collection bags will be recorded. Urine sampling, processing, storage and shipment instructions are provided in a Laboratory Manual.

When deemed appropriate at a later date, urine samples remaining after the pharmacokinetic analysis may be used for exploratory metabolic profiling or exploratory biomarker analysis after the study. These tests will be described in a separate report and will not be incorporated in the integrated CSR.

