## **9.6 Additional Conventions**

Missing conspicuity scores will be imputed per the algorithm described in [Section 9.3.2.1]. Otherwise, no imputation of missing data will be done with the exception of missing start and stop dates of AEs and concomitant medications.

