6.8 Additional Conventions

Missing data will be imputed in the following scenarios. Details are given in the respective sections.

- Likert scale conspicuity data impacted by ICE1 or ICE2 (see Sections [6.4.1.1](#) and [6.4.2](#))
- CEF data where images are reviewed and the ureter is marked as ‘not visualized’ (see Section [6.4.3](#))
- Start and stop dates of AEs and concomitant medications if they are partial or missing (see Section [6.8.2](#))
- Urine weight and volume for which a participant was unable to void (see Section [6.6](#))

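### SAP 6.6 sets every negative net urine weight to 0 g, so an interval with a measured urine concentration can be given an Ae of zero

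*SAP*

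**What the plan says.** SAP 6.6 (Analysis of Pharmacokinetics) takes net urine weight as full bag minus empty bag. It then converts to volume: "Urine volume at a time point will be calculated by dividing the urine weight in grams by 1.018". Two zero rules follow. Participants recorded as unable to void "will have their urine weight imputed as 0 g and their urine volume reported as 0 mL for the analysis". Separately, "Participants with a reported urine weight that is negative will have their urine weight imputed as 0 g". The second rule does not depend on the cause of the negative value, on its size, or on whether the bag yielded a concentration.

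The outputs that use this volume are interval Ae, cumulative Ae and urine production rate. In addition, "Ae and the percentage of ASP5354 dose excreted into urine (Ae%) during surgery will be summarized". Ae and Ae% are listed endpoints (Protocol Table 4, additional secondary; SAP 5.6.1).

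On sampling, Protocol 7.4.2 says: "Aliquots of urine samples will be collected from each collection bag". In its list of imputed data, SAP 6.8 names for urine only this case: "Urine weight and volume for which a participant was unable to void".

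**The concern.** A net urine weight cannot be negative. A negative value is therefore a weighing, tare or transcription error, not evidence that the bag was empty. If the aliquot from that bag gave a quantifiable concentration, urine was present. The rule nevertheless gives the interval the same value as a true failure to void, while SAP 6.6 still summarizes the concentration for that interval. The reported data then contradict themselves.

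The false zero does not stay in one interval. Cumulative Ae is a running sum, so every later value for that participant carries it, and so does Ae% during surgery. PK is reported in five groups, some of them small: about 13 adolescents, and 0 to 10 adults with moderate or severe impairment, split into two groups. One record can be visible in such a mean.

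**Working it through.** The plan gives no figure on this point to reproduce, so the check follows the SAP's own steps.

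**Inputs from the documents.** W = full bag minus empty bag; negative W becomes 0; V = W/1.018 (SAP 6.6). Dose = 3 mg = 3000 micrograms (Protocol Table 5).

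**Inputs assumed.** Ae = C × V, because the SAP does not print the formula. Concentrations, true urine weights, weighing-error SDs and half-life are also assumed; the documents give none of them for this purpose.

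**1. One interval under the rule.** Reported W = −2 g becomes 0 g, so V = 0/1.018 = 0 mL and Ae = C × 0 = 0 for any C.

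**2. What the interval should have contributed.** Ae% = 100 × C × (W/1.018)/3000.
- W = 1 g, C = 1 microgram/mL: V = 0.98 mL, Ae = 1.0 microgram, 0.03% of dose.
- W = 5 g, C = 5: V = 4.91 mL, Ae = 24.6 micrograms, 0.82%.
- W = 50 g, C = 20: V = 49.12 mL, Ae = 982.3 micrograms, 32.7%.

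The rule gives 0 in all three cases. For that interval the error is always downward.

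**3. Group mean, small random error.** Let the recorded weight be the true weight W plus mean-zero normal error with SD s. The mean after flooring at zero is W·Φ(W/s) + s·φ(W/s). If negatives are dropped instead, the mean of the remaining intervals is that quantity divided by Φ(W/s).

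| True W (g) | s (g) | P(negative) | Bias, floored (g) | Bias, dropped (g) |
|---|---|---|---|---|
| 1 | 3 | 0.37 | +0.76 | +1.80 |
| 2 | 3 | 0.25 | +0.45 | +1.28 |
| 5 | 5 | 0.16 | +0.42 | +1.44 |
| 10 | 3 | 0.0004 | below +0.001 | +0.005 |

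Each floored bag is too low, yet the mean is too high. The positive errors in other bags stay, while the negative errors that would have offset them are cut off at zero.

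**4. Group mean, gross error.** If full and empty weights are swapped in a share q of bags, unrelated to bag content, those bags go to zero and mean Ae falls by about q: −1%, −2% or −5% for q = 1%, 2% or 5%.

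**5. A bag holding its interval's full expected excretion.** Assume first-order, almost complete renal excretion with a half-life of 1 to 3 h. The fraction of dose excreted from a to b is exp(−ka) − exp(−kb), with k = ln 2/half-life.
- 30 to 60 min: 0.207 (1 h), 0.134 (2 h), 0.097 (3 h).
- 10 to 30 min: 0.184, 0.103, 0.071.

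One zeroed 30 to 60 min bag lowers mean Ae% by 0.097/5 to 0.207/5, or 1.9 to 4.1 percentage points, in a group of 5. In a group of 13 the loss is 0.097/13 to 0.207/13, or 0.7 to 1.6 points.

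**The case against.** A floor at zero is a common convention, and it keeps a negative volume out of Ae. Relative to using the negative weight itself, it raises Ae. Bags are changed after short intervals, the first at about 10 minutes (Protocol Table 3), so a nearly empty bag with a small weighing error is a plausible source; for that case zero is close to the truth. Querying impossible weights is ordinary data cleaning, which Protocol 10.1.8 assigns to the sponsor. SAP 6.6 already lists all PK data, and the Laboratory Manual, not available here, may cover weighing. Setting values to missing has its own bias, as step 3 shows, and a −1 g reading on the first bag could cost a participant the whole Ae%.

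Much of this stands. It removes any claim about direction at group level, and it means the fix must state its own costs. It does not rescue the unconditional rule. General data cleaning does not change what the SAP prescribes for records left negative, and a measured concentration distinguishes a bag that held urine from one that did not.

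A reader might also infer that the rule breaches SAP 6.8 and Protocol 9.6, the latter because it says "Otherwise, no imputation of missing data will be done". That reading is weak. Both sections concern missing data, whereas a negative weight is recorded but implausible, and SAP 6.8 refers to SAP 6.6 for details. The omission from the SAP 6.8 list is editorial.

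**Conclusion.** The concern holds for the interval and the participant. When a negative net weight coincides with a quantifiable concentration, the SAP produces an Ae of 0 that is too low. Other things equal, that participant's later cumulative Ae and Ae% are too low as well. This rests on Ae being concentration times volume.

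A reader might go further and infer that Ae, cumulative Ae and Ae% are understated in the group summaries, perhaps by 2 to 4 percentage points. The documents do not support that. They give no cause, size or frequency for negative weights, and they do not show that any will occur. Direction depends on the cause (steps 3 and 4). The 2 to 4 points need an assumed half-life, a bag holding its full expected content, and a group of 5.

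The reach is limited. These are descriptive PK summaries without a hypothesis test; the primary and key secondary efficacy analyses are untouched. The adolescent sample-size precision rests on plasma clearance and volume of distribution (Protocol 9.5.2). The population PK analysis has a separate plan, and whether it uses the imputed volumes is not stated.

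**What to change.** In SAP 6.6:
- Keep 0 g for 'unable to void' and for bags with no urine or no aliquot.
- For a negative net weight with a quantifiable concentration, query the full and empty bag weights and correct them where possible. A swapped pair can be recovered this way.
- If unresolved, set weight, volume and interval Ae to missing, and flag that participant's cumulative Ae and Ae% as incomplete from that interval on.
- Report the number of such intervals, and show the summaries with 0 g substituted as a sensitivity summary.

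In SAP 6.8, name the case in the list.

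The cost is a short edit to SAP 6.6, one line in SAP 6.8, a few data queries and one extra summary. There are two downsides. A few participants may lose a cumulative Ae or Ae% value, which matters most in the small groups. Removing unresolved negatives while keeping positive errors can also select the remaining intervals slightly upward. The 0 g summary shows how much the choice matters.
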